5.0 Study Subject Selection

5.1 Subject Inclusion Criteria

Cohort 1: Age \geq 18 years, English or Spanish speaking, HIV-positive, labs indicate that they are a candidate for the medication and virally suppressed, meaning that their HIV-1 ribonucleic acid is less than 50 copies per mL. Individuals enrolled in Cohort 1 must be willing to complete the locator form (Appendix G) in order to receive appointment reminders prior to their monthly/bi-monthly injection and ongoing follow-up by outreach and study staff to maximize potential for adherence.

Cohort 2: Currently enrolled in care at CID and receiving CAB-RPV LA injection, age \geq 18 years, English or Spanish speaking. Individuals enrolled must be willing to complete the locator form in order to receive appointment reminders prior to follow-up data collection.

Cohort 3: Enrolled in care at CID but not receiving CAB-RPV LA, age \geq 18 years, matched to participants demographically and in terms of other characteristics in Cohort 1 at a 1:1 ratio. Individuals in Cohort 3 will be receiving the Standard Care for HIV treatment in CID. Standard of care for this group includes access to regular appointments with their HIV provider, oral ART, case management services, etc. Individuals enrolled must be willing to complete the locator form in order to receive appointment reminders prior to follow-up data collection.

Our goal for all three cohorts is to enroll a percentage of women that is equivalent to the number of female patients served by the sites, approximately 20-30% female. Similarly, we will ensure that our sample includes individuals of color proportional to their representation within the setting across all three cohorts.

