7.2 Cohorts 2 & 3 Recruitment, Screening & Enrollment

Cohort 2 Recruitment and Enrollment: Participants for Cohort 2 will be individuals who are receiving HIV in care at BMC's Center for Infectious Diseases (CID) and are receiving CAB-RPV LA. CID pharmacists and providers will approach all individuals who are actively receiving CAB-RPV LA and assess whether they are interested in participating and ask them to complete the Screening Consent (Appendix C). If individuals are interested in participation, they will be given a warm handoff to study staff. Study staff will meet with patients at CID to complete the enrollment consent form (Appendix D). Participants will also be asked to complete the participant questionnaire at the baseline, midpoint (2-4 months post baseline) and endpoint (at least 6 months post baseline). They will also be asked to complete the Locator Form (Appendix F). Participants will enter the cohort and contribute data to the study from their first CAB-RPV LA injection and be followed in the EHR for a period at least 6 months to determine engagement in care and adherence. Data on clinical endpoints (appointment adherence, viral load, CD4, drug use etc.) will be collected from the EHR.

Cohort 3 Recruitment and Enrollment: EHR data will be used to match patients for Cohort 3 1:1 to patients in Cohort 1 based on the following variables: history of drug use, housing status, sex. Patients in cohort 3 will be a prospective cohort of patients who are HIV positive and not receiving CAB-RPV LA. The Clinical Data Warehouse will match 10 participants to every 1 enrolled in Cohort 1 based on the variables above. CID staff will approach potential participants to assess interest in participation. If individuals are interested in participating, they will be given a warm handoff to the project manager to complete the Enrollment Consent form (Appendix D). They will also be asked to complete the Locator Form (Appendix G). The remainder of their study activity will mirror that of Cohort 2.

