7.3 Data Collection

Objective 2 will include two forms of data collection: 1) participant questionnaires at enrollment (baseline), midpoint (2-4 months), and endpoint (at least 6 months post enrollment) follow-up; 2) clinical and appointment data from the EHR. The baseline questionnaire will be administered to all participants at the time of consenting to participate in the study in order to collect basic sociodemographic characteristics, such as gender identity, education, marital status, income, residence, and other characteristics shown to influence ART outcomes (Mills et al., 2006). The questionnaire will also collect data on potential predictors of intervention success, including unmet needs, satisfaction with care and stigma. (Appendix F). At the midpoint (2-4 months post enrollment) and endpoint (at least 6 months post enrollment), the data will be collected again, using the same data collection instrument. The midpoint data collection and endpoint data collection target dates will be determined by study staff and participants at the first enrollment appointment. For Cohort 1 and Cohort 2 participants, these dates will coincide with their scheduled injections if possible, for convenience.

One week before each target data collection date, study staff will contact the participant using the preferred communication method they specified on their Locator Form at enrollment. Once a data collection date has been determined, study staff will contact participant through their preferred means of communication one day prior to appointment for a reminder.

At the time of data collection, the participant and study staff will meet at determined study location (either Project Trust or CID). Study staff will bring the Participant Folder, Log Book and a ClinCard. The participant will complete the participant survey. If the participant is in Cohort 1 or 2 and is scheduled to receive their

Protocol Title: **CAB-RPV LA Implementation Strategies for High-Risk Populations**

injection at this appointment, the survey can be completed during the 15-minute observation period after the injection.

The clinical and appointment data to be collected from the EHR on all study participants will include clinical endpoints (appointment adherence, viral load, CD4, etc.). Data on clinical endpoints will be collected from their EHR at enrollment at each data collection period using the Chart Review Tool (Appendix E).

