11.2 Sample Size Calculation

For the pilot study, we have powered our study to address hypothesis 4 above. Our power calculation is as follows: With a total of 60 participants, 20 patients in each cohort, the study will have the statistical power to detect clinically meaningful differences in both engagement in care (appointment adherence) and undetectable viral load at 6 months. Depending on appointment adherence and undetectable viral load in the standard of care control group, we will be able to detect a minimum 40% difference, assuming 80% power and type 1 error probability (alpha) = 0.05. Estimates from our study sites suggest that undetectable viral load can be as low as 50% at any given time in our high-risk population. If we observe this level in the standard of care control group at 6 months, we will be able to observe a difference of 40% (or 90% vs. 50%) between the Cohort 1 CAB-RPV LA in the CBOc arm vs. the Cohort 2 CAB-RPV LA in the clinic arm and Cohort 1 CAB-RPV LA in the CBO arm vs. Cohort 3 no CAB-RPV LA arm participants, respectively. Because our intention to treat (ITT) analytic approach may mean an even lower proportion in controls (because missing data will be considered detectable), we believe our sample size is sufficient to yield rigorous clinical outcomes.

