11.3 Statistical Methods

We will first conduct exploratory analyses to assess the completeness and distributional properties of all variables, including an exploration of location (e.g., means for continuous variables and frequencies and percentages for categorical variables), spread (e.g., ranges, standard deviations), and shape (e.g., normal, skew). Missing baseline sociodemographic data will be imputed using single or multiple imputation technique if the proportion missing is $<10\%$ or $\geq 10\%$, respectively. After enrollment, we will compare dropout rates and characteristics of subjects who drop out or are lost to follow-up to assess potential for bias. In cases of missing viral load data, we will treat the result as detectable, in accordance with our primary ITT analytic approach, similar to other studies. Our primary analyses will be by ITT, but we will also conduct per protocol analyses via logistic regression models to estimate treatment effects.

Sociodemographic, behavioral, and clinical attributes at baseline will be compared between Cohort 1 and Cohort 2 and Cohort 1 and Cohort 3 using Chi Square and Fisher Exact test for categorical variables and T-test and Wilcoxon and Kruskal-

Protocol Title: **CAB-RPV LA Implementation Strategies for High-Risk Populations**

Wallis tests for continuous variables. Differences in engagement in care will be examined in two separate models to compare Cohort 1 vs Cohort 2 and Cohort 1 vs. Cohort 3. We will construct a multivariable logistic regression model with a logit link and the events/trials syntax to model the outcome. The inclusion of key baseline variables for adjustment will be based on a p value of ≤ 0.2 in the bivariate analysis or clinical significance. The following regression equation will be used:

$$\text{Engagement in care} = \alpha + \beta_1 * \text{ixgroup}_1 + \beta_2 * \text{factor}_1 + \dots + \beta_n * \text{factor}_n + \varepsilon,$$

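### In the Cohort 1 vs Cohort 2 models, baseline values are pre-injection in one cohort and on-treatment in the other; 11.3 allows adjustment for them, which can bias the site comparison in an unknown net direction

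*Combined protocol and SAP*

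**What the plan says.** **Adjustment rule.** Section 11.3 compares sociodemographic, behavioral and clinical attributes at baseline between Cohorts 1 and 2. It then models engagement in care by logistic regression in events/trials form, separately for Cohort 1 vs 2 and Cohort 1 vs 3. On covariates it says: "The inclusion of key baseline variables for adjustment will be based on a p value of" 0.2 or less in a bivariate analysis, or on clinical significance. It names no covariates. Six-month undetectable viral load follows the same approach.

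**When baseline is measured.** Section 7.3: "The baseline questionnaire will be administered to all participants at the time of consenting to participate in the study". EHR clinical data are also taken at enrolment. The questionnaire covers "potential predictors of intervention success, including unmet needs, satisfaction with care and stigma". Section 10.1 says abstracted clinical information will serve as covariates.

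**Treatment status on that day.** Section 7.1 says Cohort 1 cannot be injected on the day of enrolment. Section 5.1 defines Cohort 2 as "Currently enrolled in care at CID and receiving CAB-RPV LA injection", and the regimen table in section 7.0 anticipates a maintenance dose for Cohort 2 in Month 1.

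**A different clock for Cohort 2.** Section 7.2: "Participants will enter the cohort and contribute data to the study from their first CAB-RPV LA injection". Section 11.3 does not say which of the two starting points defines baseline.

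**The concern.** An adjuster should be measured before the exposure it helps to compare. Here the same variable is pre-treatment in Cohort 1 and on-treatment in Cohort 2. If injections change it, part of the difference between cohorts reflects timing and not case mix. Adjusting for it then treats that timing difference as a pre-existing imbalance.

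Cohort 1 vs Cohort 2 is the only contrast in which both groups receive CAB-RPV LA and the delivery site differs, so it is the comparison a reader would use to judge the community site itself. The stated rule could produce or hide a site difference when the sites perform alike.

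**Working it through.** **1. The plan's own figure.** Section 11.2 gives "With a total of 60 participants, 20 patients in each cohort", "assuming 80% power and type 1 error probability (alpha) = 0.05", for 90% vs 50%. Taking a two-sided test with pooled variance:

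n = [1.96 × √(2 × 0.7 × 0.3) + 0.842 × √(0.9 × 0.1 + 0.5 × 0.5)]² / 0.4² = (1.270 + 0.491)² / 0.16 = 19.4, so 20 per cohort.

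This reproduces, with 81.3% power. It does not depend on the covariate question. It does give the scale: 20 vs 20, with a 40-point detectable difference.

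**2. Size for one covariate.** Suppose there is no site effect. Each person's log-odds of success on injections is a + bX, where X is the pre-injection value. Cohort 1 is measured at X and Cohort 2 at X + δ. Adjusting for the measured value leaves a cohort coefficient of bδ, so the false odds ratio (Cohort 1 vs Cohort 2) is (odds ratio per SD)^δ. Both inputs are assumptions; the documents give neither.

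| Shift δ (SD) | Odds ratio 2 per SD | Odds ratio 3 per SD |
|---|---|---|
| 0.3 | 2^0.3 = 1.23 | 3^0.3 = 1.39 |
| 0.5 | 2^0.5 = 1.41 | 3^0.5 = 1.73 |
| 0.8 | 2^0.8 = 1.74 | 3^0.8 = 2.41 |

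Simulation agrees with these values. If Cohort 2 succeeds 80% of the time (odds 4), the extremes correspond to 4 × 1.23 / (1 + 4 × 1.23) = 83% and 4 × 2.41 / (1 + 4 × 2.41) = 91% in Cohort 1, a false gain of 3 to 11 points. A negative δ inverts the odds ratio.

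**3. Would the screen pick such a covariate?** If the screen is against cohort, a 0.5 SD shift at 20 vs 20 has expected z = 0.5 × √10 = 1.58. The two-sided 0.2 cut-off is 1.28. The chance of selection is about Φ(0.30) = 62%. If bivariate means association with the outcome, this figure does not apply.

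**4. False-positive rate at 20 vs 20.** The shifts and odds ratios are those of step 2, with 80% success at the covariate mean and no site effect. By simulation the nominal 5% test rejects about 3% to 14% of the time for a binary outcome. For events/trials engagement with an assumed 6 appointments each, it rejects about 10% to 68% of the time.

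**5. Net direction.** This is a large simulation with 200,000 per cohort before selection and no site effect. Log-odds of success are 0.8 + 0.8 × pre-injection status, measurement noise has SD 0.5, and the shift applies to Cohort 2's baseline only. The entries are adjusted odds ratios; the truth is 1.

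| Situation in Cohort 2 | Shift −0.25 | 0 | +0.25 | +0.5 |
|---|---|---|---|---|
| No selection, no head start | 0.85 | 1.01 | 1.18 | 1.38 |
| Only 60% persist to enrolment, selectively | 0.79 | 0.91 | 1.08 | 1.24 |
| Head start of 0.4 log-odds | 0.58 | 0.68 | 0.78 | 0.92 |

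Along each row, a favourable shift raises the estimate, which is the mechanism at issue. Down the columns, the other two features of Cohort 2 can cancel or reverse it. These settings are also assumptions; only the pattern should be relied on.

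**The case against.** A reader might infer that the plan is tilted towards the community site. The documents do not support that. Cohort 2 members are current users who stayed on injections until enrolment and will have been on treatment longer by month 6. Both features can favour the clinic, and step 5 shows the sign changing.

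A reader might also say that the models do adjust for on-treatment values. Section 11.3 names no covariates, and several questionnaire items (gender identity, education, marital status) are not plausibly changed by injections. The defect is that nothing excludes the items that could be.

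Baseline viral suppression is a weak example. The Protocol Summary and section 5.2 require it at enrolment and before starting CAB in both injection cohorts, so it hardly varies. CD4, appointment adherence and the self-reported scales carry the point.

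Section 7.2 can be read as aligning the cohorts, with Cohort 2's EHR baseline at the first injection. That could cure the EHR values if 11.3 said so. It cannot cure the questionnaire, which exists only from consent and on that clock falls inside Cohort 2's follow-up.

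A linear model of a continuous score under similar assumptions gives a type I error of 15% to 31%. That figure should not be used, because 11.3 contains no linear model and specifies no analysis for the satisfaction hypothesis H5.

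Finally, restricting the adjusters does not always bring the estimate nearer the truth. In the head-start row the unshifted covariate gives 0.68, while the +0.5 SD covariate gives 0.92. That is two errors partly cancelling and is no reason to keep either, but it shows that the restriction alone does not make the contrast unbiased.

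**Conclusion.** The point holds in a limited form. Enrolment baseline is not comparable between Cohorts 1 and 2, section 7.2 gives Cohort 2 a second starting point, and 11.3 admits treatment-affected adjusters. The adjusted site comparison can therefore be biased. A covariate that injections improve pushes it towards the community site and one they worsen pushes it away. The net direction is unknown.

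The odds ratios of 1.23 to 2.41 are illustrations that rest on assumed shifts of 0.3 to 0.8 SD and covariate odds ratios of 2 to 3 per SD. The resulting 3 to 11 points are well below the 40-point detectable difference. The distortion matters most for events/trials engagement, where each person contributes several appointments.

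H3 and H4, including the hypothesis that sets the sample size, compare Cohort 1 with Cohort 3 and are untouched. This is a worthwhile correction at low cost and does not threaten the main result.

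**What to change.** In section 11.3:

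- State one time zero for Cohort 2 and reconcile sections 5.1, 7.0 and 7.2 with it.
- For every Cohort 1 vs Cohort 2 model, adjust only for characteristics that injections cannot change (such as age, sex, race/ethnicity, education, drug use history) and for EHR values dated on or before each person's first CAB-RPV LA injection.
- Do not adjust this contrast for enrolment satisfaction, stigma or unmet needs, or for on-treatment CD4, viral load or appointment adherence.
- Report Cohort 2's time on injections before enrolment, and state that the restriction does not remove prevalent-user selection.

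The cost is SAP wording plus abstraction of Cohort 2's EHR covariates at the first-injection date; section 10.1 says injections are recorded in the EHR. No extra participants or visits are needed. There are two small losses: self-reported items can no longer serve as adjusters in this contrast, and pre-injection EHR history may be incomplete for Cohort 1 participants new to the medical center.

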11.0 Statistical Plan

11.1 Study Hypotheses

Objective 2 has the following hypotheses:

- **H1:** Changing the service site will result in $\geq 80\%$ of participants in the community-based intervention arm beginning injections
- **H2:** Of participants in the community-based intervention arm who begin injections, 80% will complete 6 injections
- **H3:** Changing the service site will result in improved engagement in care for participants in the community-based intervention arm compared to matched controls (Cohort 3) at 6 months for intervention patients compared to control group patients
- **H4:** Changing the service site will result in superior HIV viral suppression at 6 months compared to for participants in the community-based intervention arm compared to matched controls (Cohort 3)
- **H5:** Participants in the community-based intervention arm will be equally satisfied with their care compared to patients who receive care in clinic settings (Cohort 2).

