where ixgroup_1 is a dummy variable for cohort assignment, α is the intercept, $\beta_1, \beta_2, \dots, \beta_n$ is a vector of possible coefficients, and ε is an error term. Similarly to examine adherence we will use a multivariable logistic regression with a dichotomous outcome for undetectable viral load status at 6 months. Potential confounders will be examined using methods described above and entered into the final model based on a p value of ≤ 0.2 or clinical significance. We will conduct stratified analyses based on gender and other risk attributes (e.g. homelessness, substance use, etc.), though this will be exploratory, given the cohort study's pilot nature and our sample size.

12. Budget Justification

Our total enrollment into Objective 2 remains 60 participants. Therefore, the resources necessary to accomplish the scope remain unchanged, and we are not requesting a budget increase.

13. Ethics/Protection of Human Subjects

This study will be conducted according to applicable US federal regulations and institutional policies (which are based in federal regulations, guidance, and ICH Good Clinical Practice guidelines). This protocol and any amendments will be submitted to the Boston Medical Center/Boston University Medical Campus IRB, for formal approval of the study conduct. The decision of the IRB concerning the conduct of the study will be made in writing to the investigator.

All subjects for this study will be provided a consent form describing this study and providing sufficient information for subjects to make an informed decision about their participation in this study. The consent form will be submitted with the protocol for review and approval by the IRB. The consent of a subject, using the IRB-approved consent form, must be obtained before that subject is submitted to any study procedure. Consent will be documented as required by the IRB.

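### Section 11.3 names no test of the cohort coefficient for H4 and no method for a cohort with no detectable results; power at the plan's own rates runs from about 69% to 84% depending on that choice

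*Combined protocol and SAP*

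**What the plan says.** Section 11.1 states H4 as a superiority claim: "Changing the service site will result in superior HIV viral suppression at 6 months", for Cohort 1 against the matched controls in Cohort 3. Section 11.2 makes it the basis of the sample size: "we have powered our study to address hypothesis 4 above". The size is fixed as "With a total of 60 participants, 20 patients in each cohort", and the claim is that "we will be able to detect a minimum 40% difference, assuming 80% power and type 1 error probability (alpha) = 0.05". The control rate comes from site estimates that "undetectable viral load can be as low as 50% at any given time in our high-risk population", and the worked case is 90% vs 50%. Section 11.2 names no test and does not say whether alpha is one- or two-sided.

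Section 11.3 then gives the analysis: "we will use a multivariable logistic regression with a dichotomous outcome for undetectable viral load status at 6 months". Covariates enter on a p-value threshold of 0.2 or on clinical grounds, so their number is not fixed. A missing viral load counts as detectable in the primary intention-to-treat analysis, so the denominator stays at 20 per cohort. Nothing in 11.1 to 11.3 says whether the cohort coefficient is judged by a Wald, likelihood-ratio, score, exact or penalised test. Nothing says what interval is reported, or what is done if every patient in a cohort has the same result.

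**The concern.** With 20 patients and an expected success rate of 90%, Cohort 1 is expected to have only 2 detectable results (20 × 0.10) and may have none. If it has none, the maximum-likelihood odds ratio is infinite, the printed standard error becomes meaninglessly large and the Wald p-value goes to about 1. This is separation. It arises with cohort as the only term in the model, so naming or limiting covariates in advance does not remove it.

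The outcome that favours the intervention most strongly is therefore the one that the default output cannot assess. Because the plan is silent, the choice between tests with quite different power would be made after the data are seen, for the only hypothesis on which the study is sized. An analyst who met separation would have no pre-specified fallback, and any rescue could look chosen for its result.

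**Working it through.** **Inputs.** 20 vs 20, 90% vs 50%, power 80%, alpha 0.05 (section 11.2); logistic model, missing counted as detectable (section 11.3). Assumed here: two-sided alpha, no covariates, matching ignored.

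**1. The plan's own figure.** For a two-proportion z test with pooled null variance, p̄ = (0.9 + 0.5)/2 = 0.7.

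- n = [1.96·√(2 × 0.7 × 0.3) + 0.842·√(0.9 × 0.1 + 0.5 × 0.5)]² / 0.4² = 19.4, so 20 per cohort.
- Power at n = 20: Φ[(0.4 − 1.96·√(2 × 0.21/20)) / √(0.34/20)] = Φ(0.889) = 81.3%.

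The stated 80% reproduces.

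**2. Chance of separation.** P(no detectable results in Cohort 1) = p²⁰: 0.9²⁰ = 0.122 and 0.95²⁰ = 0.358.

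**3. Power of the logistic cohort coefficient.** A rough Wald check uses the expected table, 18/2 vs 10/10. The log odds ratio is ln 9 = 2.197. Its standard error is √(1/18 + 1/2 + 1/10 + 1/10) = 0.869, so z = 2.528 and power is about Φ(2.528 − 1.96) = 71%.

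The exact figures sum Binomial(20, p₁) × Binomial(20, p₂) over all 21 × 21 outcomes with p ≤ 0.05. For the Wald test, a table with a zero cell counts as non-significant.

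| Cohort 1 vs control | Wald | Likelihood ratio | Pearson (score) | Fisher exact |
|---|---|---|---|---|
| 85% vs 50% | 61.8% | 69.4% | 69.4% | 57.3% |
| 90% vs 50% | 69.1% | 83.8% | 83.8% | 74.2% |
| 95% vs 50% | 57.0% | 94.5% | 94.4% | 89.4% |
| 98% vs 50% | 30.8% | 98.5% | 98.5% | 96.4% |

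Against a 50% control rate, Wald power peaks near a Cohort 1 rate of 90% and then falls. The other tests keep rising. At 90% vs 50% the Wald test would need 24 to 25 per cohort (79.9% and 82.5%).

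**4. One table worked through: 20/20 vs 14/20.**

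- Wald: p goes to about 1, because the odds ratio is infinite.
- Pearson: (0.30)² / (0.85 × 0.15 × 2/20) = 7.06, p = 0.008.
- Likelihood ratio: 2 × [14 ln 0.7 + 6 ln 0.3 − 34 ln 0.85 − 6 ln 0.15] = 9.38, p = 0.002.
- Firth: without covariates the penalty adds one half to each cell. The fitted rates are 20.5/21 and 14.5/21, and the common rate is 35/42. The penalised statistic is 2 × [20.5 ln(20.5/21) + 0.5 ln(0.5/21) + 14.5 ln(14.5/21) + 6.5 ln(6.5/21) − 35 ln(35/42) − 7 ln(7/42)] = 7.14, p = 0.008.

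**5. Type I error, same enumeration, both cohorts at the same rate.**

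| Common rate | Ordinary likelihood ratio | Firth penalised likelihood ratio |
|---|---|---|
| 50% | 4.3% | 3.9% |
| 70% | 5.3% | 4.5% |
| 80% | 5.5% | 4.9% |
| 90% | 8.5% | 3.9% |

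Firth power at 90% vs 50% is 82.2%.

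**6. With covariates.** The plan does not fix their number. In simulations with three binary covariates (an assumption; 2,000 trials per setting), type I error of the ordinary likelihood-ratio test was 7.0%, 7.2% and 10.1% at common rates of 70%, 80% and 90%. Firth had 82% power at 90% vs 50%.

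**The case against.** A reader might infer that the planned analysis has 69% power and misses the stated 80%. The documents do not support that. They never name a Wald test; that it is the usual default is a statement about software. The likelihood-ratio test of the same logistic model has 83.8% power at 90% vs 50% and gains power as Cohort 1 improves. The plan's 80% is arithmetically sound for a comparison of two proportions.

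A reader might also infer that a 20/20 result would be declared non-significant. It could be, but an estimate with a standard error near 18,000 (as fitted for 20/20 vs 10/20) is conspicuous, and a careful analyst would probably look for another test.

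The extreme rates are not plan assumptions either. Counting missing results as detectable makes 20/20 less likely, and the population is selected for risk of leaving care. At 80% vs 40% the choice matters little: Wald 72%, likelihood ratio 75%, and about a 1% chance of no detectable results in Cohort 1. If controls fall to 40% with Cohort 1 at 90%, even Wald reaches 82%. The ordinary likelihood-ratio test is inflated mainly near the ceiling, and the adjusted figures rest on assumed covariates.

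All of this stands, and it limits the point to under-specification. It does not remove the 12% chance of separation at the plan's own 90%, the spread in power between tests, or the lack of a fallback. Choosing the ordinary likelihood-ratio test would restore the power, but not alpha when both cohorts do well.

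**Conclusion.** The point holds as a gap in specification. For the one powered hypothesis, at the plan's own 90% vs 50% with 20 per cohort, power is about 69% under Wald and about 84% under the likelihood-ratio test. There is a 12% chance of no detectable results in Cohort 1, or 36% if its true rate is 95%. Neither ordinary test is satisfactory throughout: Wald loses power at high Cohort 1 rates, and the likelihood-ratio test has 8.5% type I error when both cohorts are at 90%. A Firth penalised test has about 82% power and at most 4.9% type I error at the common rates of 50% to 90% that were tried.

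These figures assume a two-sided 0.05 test and an unadjusted model, and they ignore the 1:1 matching. About 12 detectable results are expected among the 40 patients (2 + 10), so covariates could make sparse data worse. This is a worthwhile, cheap improvement to a pilot analysis.

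**What to change.** In section 11.3, state that the viral-load models (Cohort 1 vs 3, and Cohort 1 vs 2 if modelled) are fitted by Firth penalised logistic regression, and that the penalised likelihood-ratio p-value and profile-likelihood interval for the cohort coefficient decide H4. Add that the difference in percentage undetectable is reported with a score (Miettinen-Nurminen) interval, since section 11.2 plans on that scale. State whether alpha is two-sided.

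The 11.2 power can then stand. It needs restating, as about 69%, only if Wald output is to decide H4.

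The cost is two or three sentences and one software option, with no extra patients or data. The downside is slightly less power than the ordinary likelihood-ratio test (about 82% against 84% at 90% vs 50%). The change should be made before outcome data are analysed.
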